Evaluations consists of vital signs, laboratory assessments blood examination, device (ICD or CRTD/P) interrogation, 24h' Holter ECG in case of ICD/CRTD/P malfunction as a backup arrhythmia assessment and echocardiography. Patient's glucose level will be monitored by a home device 3 times a day in the first week and thereafter once a week or as needed. At visit 2, an endocrinologist consultant will give to the patient instructions for antidiabetic treatment titration according to [appendix 1](#).

Patients will be treated for up to 8 weeks with the study drug or placebo 10 mg/day every morning.

Washout period

Study subjects will stop study drug (empagliflozin/placebo) of the first treatment period and will be given placebo for a washout period of 4 weeks and will crossover to the second drug at the end of this period at the beginning of the next treatment period. During this period, patient's glucose level will be monitored by a home device 3 times a day in the first week and thereafter once a week or as needed. Safety laboratory examinations, HbA_{1c}, device interrogation and resetting, Holter ECG and echocardiography will be performed at the end of this period (visit 3). In the case of abnormal glucose levels during the washout period, diabetes treatment will be changed according to appendix 1 aiming to maintain glucose levels at normal range.

Second treatment period

Patients will crossover to empagliflozin or placebo treatment for a period of 8 weeks.

Evaluations consists of vital signs, laboratory assessments including pregnancy test for FCBP. Patient's glucose level will be monitored by a home device 3 times a day in the first week and thereafter once a week or as needed. Device (ICD or CRTD/P) interrogation and 24h' Holter ECG in case of ICD/CRTD/P malfunction as a backup arrhythmia assessment and echocardiography. In the case of abnormal glucose levels during the second treatment period, diabetes treatment will be changed according to appendix 1 aiming to maintain glucose levels at normal range.

Patients will be treated for up to 8 weeks with the study drug or placebo 10 mg/day every morning.

Medication compliance will be performed during the two treatment periods by counting the returned study drug blisters.

Accompanying scientific program

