4.2.1 Visit schedule and assessments

Table 2 visit schedule and assessments

Trial Period	Screening	Treatment Period			
Visit	1	2	3	4	5
Study Week	0	8	16	20	28
Days from randomization	-56	0	56	84	140
Informed Consent	X				
Inclusion/Exclusion Criteria	X	X			
Medical History	X				
Concomitant therapy	X	X	X	X	X
Demographics	X				
Physical Exam	X	X			
Vital Signs	X	X	X	X	X
Height	X				
Weight	X	X	X	X	X
Randomization		X			
Pregnancy test ¹	X	X		X	X
Home Blood glucose monitoring ²		X	X	X	X
Safety blood samples ³	X	X	X		X
HbA _{1c}	X		X		X
Device Interrogation	X	X	X	X	X
Monitor Counter Reset	X	X	X	X	X
12 Lead Holter ECG for 24hrs		X	X		X
Echocardiography	X ⁴	X	X		X
NT-Pro-BNP		X	X	X	X
Medication Compliance check			X		X

¹ For female patients with childbearing potential (Urine pregnancy test).

[figure not shown]
² Patients without means for daily home blood glucose monitoring will be given a device on visit 2. Glucose level will be measured 3 times a day in the first week and thereafter once a week or as needed. Additional measurements are warranted in the case of hypo- or hyperglycemia signs or symptoms.

³ Safety blood samples include: Fasting blood samples (8hr fasting), Liver and kidney functions, urine dipstick for signs of infection and ketoacidosis (if positive leukocyte esterase (WBC) or nitrites a midstream urine sample for urine culture will be taken.

⁴ Echocardiography will be done if needed to verify patient suitability for inclusion criteria.

Trial Period	Screening	Treatment Period			
Visit	1	2	3	4	5
Study Week	0	8	16	20	28
Days from randomization	-56	0	56	84	140
Endocrinologist consult		X			
Biobank samples		X	X	X	X
Urine Analysis (Electrolytes)		X	X	X	X
24hr Urine Sample collection		X	X	X	X
CardioPulmonary Exercise Test & 6 minute walk distance ⁵		X	X		X
Adverse events		X	X	X	X

Study scheme

Visit 3
Analysis 1

Visit 5
Analysis 2

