Collection of information on standard of care treatment will be done as part of medications records during the study.

17. Invite study subject to study site for Holter ECG installation in one of the 7 days before the next visit.

Base line visit (2) (day 0 ±7 days)

1. Patient's enrollment. Eligibility for the study according to inclusion and exclusion criteria will be rechecked but lab tests not repeated) if all criteria are fulfilled and there is no significant change in the subject's health, he/she will be enrolled into the study to receive the first study drug.
2. Get patient randomization number.
3. Begin study drug treatment (active or placebo), provide patient 60 tablets and give treatment instructions for home use.
4. Perform a complete physical examination.
5. Measure vital signs in order to ensure compliance with study criteria. Vital signs measurements will include systolic and diastolic blood pressure, pulse rate, respiratory rate, and body temperature. Body weight will also be measured. Measurements that may potentially constitute future adverse events (e.g. hypertension, fever etc.) should be graded in the medical history form at baseline according to CTC as described in [8.1.3 below](#)
6. Collect safety blood and urine samples. Including hematology and chemistry blood examinations and urine dipstick for signs of ketoacidosis or infection.
7. Review menopausal status and in women of childbearing potential perform a urine pregnancy test (β -HCG).
8. Collect home diary glucose results and provide a new diary for the following period.
9. Provide home diary for daily blood glucose determination.
10. Perform device interrogation.
11. Perform Monitor counter reset.
12. Collect Holter ECG device results and invite study subject to study site for Holter ECG installation in one of the 7 days days before the next visit.
13. Perform echocardiography for determination of EF
14. Consult endocrinologist for glucose lowering medication titration
15. Collect blood examination for NT-Pro-BNP
16. Collect urine and blood examination for biobank sample
17. Collect urine for electrolyte concentration

18. Obtain 24 hours urine sample collection
19. Perform cardiopulmonary exercise test (In case of inability to perform cardiopulmonary exercise test according to clinical judgment, patient will have a 6 minute walk distance test)
20. Perform 6 minute walk distance
21. Review concomitant medications.
22. Document adverse events.

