Treatment washout visit (3) (day 56 ±7 days)

1. Provide patient with 30 tablets of study drug for home use
2. Collect study drug blisters returned by patient.
3. Measure vital signs in order to ensure compliance with study criteria. Vital signs measurements will include systolic and diastolic blood pressure, pulse rate, respiratory rate, and body temperature. Body weight will also be measured.
4. Collect safety blood and urine samples. Including hematology and chemistry blood examinations and urine dipstick for signs of ketoacidosis or infection.
5. Remind patient to follow the endocrinologist instructions given on visit 2.
6. Collect venous blood that will be drawn for HbA1c.
7. Collect home diary glucose results and provide a new diary for the following period.
8. Perform device interrogation.
9. Perform Monitor counter reset.
10. Collect Holter ECG device results and invite study subject to study site for Holter ECG installation in one of the 7 days days before the next visit.
11. Perform echocardiography for determination of EF
12. Collect blood examination for NT-Pro-BNP
13. Collect urine and blood examination for biobank sample
14. Collect urine for electrolyte concentration
15. Obtain 24 hours urine sample collection
16. Perform cardiopulmonary exercise test (In case of inability to perform cardiopulmonary exercise test according to clinical judgment , patient will have a 6 minute walk distance test)

17. Perform 6 minute walk distance
18. Review concomitant medications.
19. Document adverse events.

Treatment visit (4) (day 84 ±7 days)

1. Provide patient with 60 tablets of study drug for home use
2. Collect study drug blisters returned by patient.
3. Measure vital signs in order to ensure compliance with study criteria. Vital signs measurements will include systolic and diastolic blood pressure, pulse rate, respiratory rate, and body temperature. Body weight will also be measured.
4. Review menopausal status and in women of childbearing potential perform a urine pregnancy test (β -HCG).
5. Remind patient to follow the endocrinologist instructions given on visit 2.
6. Collect home diary glucose results and provide a new diary for the following period.
7. Perform device interrogation.
8. Perform Monitor counter reset.
9. Collect blood examination for NT-Pro-BNP
10. Collect urine and blood examination for biobank sample
11. Collect urine for electrolyte concentration
12. Obtain 24 hours urine sample collection
13. Review concomitant medications

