14. Document adverse events.

End of Study visit (5) (day 140 ±7 days)

- 1.
2. Collect study drug blisters returned by patient.
3. Measure vital signs in order to ensure compliance with study criteria. Vital signs measurements will include systolic and diastolic blood pressure, pulse rate, respiratory rate, and body temperature. Body weight will also be measured.
4. Collect safety blood and urine samples. Including hematology and chemistry blood examinations and urine dipstick for signs of ketoacidosis or infection.
5. Review menopausal status and in women of childbearing potential perform a urine pregnancy test (β -HCG).
6. Collect venous blood that will be drawn for HbA1c.

7. Collect home diary glucose results.
8. Perform device interrogation.
9. Perform Monitor counter reset.
10. Collect Holter ECG device results.
11. Perform echocardiography for determination of EF
12. Collect blood examination for NT-Pro-BNP
13. Collect urine and blood examination for biobank sample
14. Collect urine for electrolyte concentration
15. Obtain 24 hours urine sample collection
16. Perform cardiopulmonary exercise test (In case of inability to perform cardiopulmonary exercise test according to clinical judgment , patient will have a 6 minute walk distance test)
17. Perform 6 minute walk distance.
18. Review concomitant medications.
19. Document adverse events.

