4.4.2 Study drug interruption

No study drug interruption is allowed unless for safety reasons.

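### Visits 3, 4 and 5 float independently from randomisation, so the stated 4-week washout and on-drug end-of-period measurements are not secured

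*Combined protocol and SAP*

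**What the plan says.** Table 2 (section 4.2.1) counts visits in "Days from randomization": 0, 56, 84 and 140 for visits 2 to 5. Section 4.2.2 gives each a window of 7 days either way, for example "Treatment visit (4) (day 84 ±7 days" and "End of Study visit (5) (day 140 ±7 days" (closing brackets omitted).

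The supply is fixed by visit:
- Visit 2: "Begin study drug treatment (active or placebo), provide patient 60 tablets and give treatment instructions for home use".
- Visit 3, for the washout: "Provide patient with 30 tablets of study drug for home use".
- Visit 4: "Provide patient with 60 tablets of study drug for home use".

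Dosing is once daily (section 4.3.1). Section 4.2 describes treatment of up to 8 weeks per period and says that between periods patients "will be given placebo for a washout period of 4 weeks". Section 4.7 limits dispensing to an 8-week supply.

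No section ties visit 4 to the actual visit 3 or visit 5 to the actual visit 4, sets a minimum washout, or gives a resupply rule.

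**The concern.** When consecutive visits each have their own window around a common origin, the two windows add in the interval between them. An interval meant to be 28 or 56 days can then vary by 14 days either way, while the tablet supply has only 4 days of slack over 56.

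Two things follow. The washout can be well short of 4 weeks with every visit in window. A treatment period can also outlast its tablets, so the measurements that close it are made off drug. The exposed measurements are NT-proBNP and echocardiography at visits 3 and 5, and the 24-hour Holter from one of the last 7 days, which replaces the device count when the counter cannot be read (section 7.1). Off-drug values in an empagliflozin period would tend to move towards placebo values and blur the contrast.

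**Working it through.** **Inputs.** Visit windows from section 4.2.2: visit 3 on days 49–63, visit 4 on days 77–91, visit 5 on days 133–147. Tablets are 60, 30 and 60, one a day. Day 0 is taken as the actual randomisation visit (visit 2), with the first tablet that day.

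**The plan's own figures.** Nominal washout is 84 − 56 = 28 days. Nominal treatment periods are 56 − 0 = 56 and 140 − 84 = 56 days. The stated 4 and 8 weeks reproduce.

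**In-window ranges.**

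| Interval | Shortest | Longest | Tablets | Largest shortfall |
|---|---|---|---|---|
| Period 1 | 49 | 63 | 60 | 63 − 60 = 3 days |
| Washout | 77 − 63 = 14 | 91 − 49 = 42 | 30 | 42 − 30 = 12 days |
| Period 2 | 133 − 91 = 42 | 147 − 77 = 70 | 60 | 70 − 60 = 10 days |

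For a fully adherent patient, days free of empagliflozin are visit 4 − min(visit 3, 60), so the minimum is 77 − 60 = 17. It would be 21 if dosing stopped at 56 days, and 14 if missed doses made the tablets last to day 63.

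**How often.** The documents give no visit timing, so these shares rest on assumed patterns.

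*Independent and uniform over the window.*
- Period 1 exceeds 60 days on 3 of 15 visit days: 20.0%.
- Period 2 exceeds 60 days in 55 of 225 combinations: 24.4%.
- With 1:1 sequences, empagliflozin periods that run out: (20.0 + 24.4)/2 = 22.2%.
- Mean shortfall when it happens: 2.0 days (period 1) and 4.0 days (period 2).
- Drug-free gap of 21 days or less: 30/225 = 13.3%. It matters only for empagliflozin-first, so 6.7% of patients.
- The 17-day gap: 4/225, halved to 0.9%. The 10-day shortfall: 1/225.

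*Independent, SD 3 days, truncated to the window.*
- Run-out: (6.1 + 13.6)/2 = 9.8%.
- Mean shortfall: 1.6 and 2.5 days.
- Gap of 21 days or less, empagliflozin-first: 2.2%.

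*Visits 4 and 5 shift fully with visit 3.* Period 2 is always 56 days and the gap is at least 28, so only period 1 can overrun: 20.0%/2 = 10% (SD 3: 6.1%/2 = 3%).

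**Backup Holter.** With the Holter day uniform over the 7 days before the visit, a Holter that is needed falls off drug in 9.5% of empagliflozin periods (SD 3: 3.1%). The unconditional share is smaller and unknown.

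**Primary endpoint.** The device counter covers the whole period. With uniform timing, 1.07% of empagliflozin days are untreated. If the effect vanished at once on those days, a difference of 10 would become 10 × (1 − 0.0107) = 9.89. With the plan's SD of differences of 40 and 128 patients, power goes from 0.801 to 0.793. With SD 3, 0.35% of days are untreated and power is 0.799.

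**The case against.** A ±7-day window is routine, and sites usually book the next visit from the last one. The 17-day gap and 10-day shortfall are corner cases, and if later visits move with visit 3 no gap falls below 28 days. All of this stands, and the ranges above are limits, not expectations. But nothing in the protocol tells sites to chain visits, and even with chaining period 1 can outlast its tablets.

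There are also safeguards. Patients come to the site for Holter fitting in the week before visits 3 and 5, when a shortfall could be noticed. NT-proBNP is measured and the counter reset at visit 4, so residual effect on NT-proBNP can be seen and washout days stay out of the period 2 PVC count. Tablet counts (sections 4.7 and 6.3) and the carry-over test (section 9.2.1) can reveal a problem. These help with detection. None sets a minimum washout or a resupply, and echocardiography has no visit 4 value.

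A reader might infer that running out breaches section 4.4.2: "No study drug interruption is allowed unless for safety reasons". The documents do not clearly support that. Treatment is planned for up to 8 weeks per period (section 4.2) and up to 16 weeks in all (section 6.1), so a patient whose 60 tablets are finished has completed the stated course.

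A reader might also infer that a short washout will cause carry-over. The documents give no offset time for the drug's effect, so this is not shown either way.

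**Conclusion.** The schedule as written does not secure the 4-week washout or on-drug measurements at the end of each treatment period. The ranges (washout 14–42 days, periods 49–63 and 42–70 days on 60 tablets) follow directly from the protocol, with randomisation as day 0. Section 4.2.2 also gives visit 2 itself a ±7-day window. If day 0 is a scheduled date rather than the actual visit, period 1 widens to 42–70 days and the shares above would change.

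The consequence is small. About 3% to 22% of empagliflozin periods run out, depending on assumed timing, by a few days on average. NT-proBNP and echocardiography are only summarised by treatment (section 9.2.1), so no planned test of them is compromised. The Holter matters only when the device cannot be read, and the primary device count loses almost nothing. This is a minor point, worth making because the remedy is nearly free.

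**What to change.** Tie each visit to the actual date of the previous one:
- Visit 3 at 56 days (−7/+4) after the actual visit 2.
- Visit 4 at 28 to 35 days after the actual visit 3.
- Visit 5 at 56 days (−7/+4) after the actual visit 4.

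Treatment periods are then 49–60 days, covered by the 60 tablets already dispensed, and the washout is never under 28 days. Dispense 35 placebo tablets for the washout instead of 30. Align the 8-week supply wording in section 4.7 with the 60 tablets given, and treat the 8 and 16 weeks in sections 4.2 and 6.1 as nominal, since 2 × 60 = 120 tablets already exceed 16 × 7 = 112 days.

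The latest visit 5 becomes 60 + 35 + 60 = day 155, against 147 now. With 56 screening days that is 211 days, within the stated 6–7 months. Keeping ±7 days and dispensing 63 tablets would also prevent run-out. However, it allows 126 days (18 weeks) on tablets and a latest visit 5 of day 161, or 217 days in all (about 7.1 months).

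The cost is protocol wording, a tighter upper visit window and 5 more placebo tablets per patient. Actual washout days and days on tablets can be reported from visit dates and tablet counts already collected. No extra analysis is needed.

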4.3 Trial treatment

4.3.1 Investigational therapy

Empagliflozin and placebo is supplied to the study investigators by the Boehringer Ingelheim Company via the sponsor. Empagliflozin is supplied as 10 mg tablets packaged in blister packs.

Labels will comply with the legal requirements of Israel and be printed in Hebrew, Arabic and English. The storage conditions for study drug will be described on the medication label. Patients will receive study drug 10mg by the oral route q.d. if in the opinion of the investigator the patient is benefiting from treatment with this study drug, and in the absence of any safety concerns. Treatment will be withheld only in the case of limiting toxicities.

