First treatment period

Randomization will take place after obtaining patient's informed consent and after fulfilling the inclusion and exclusion criteria. Patients will be assigned to empagliflozin or placebo treatment for a period of 8 weeks by a central randomization process.

Evaluations consists of vital signs, blood tests, device (ICD or CRTD/P) interrogation, 24h' Holter ECG in case of ICD/CRTD/P malfunction as a backup arrhythmia assessment and echocardiography. Patient's glucose level will be monitored by a home device 3 times a day in the first week and thereafter once a week or as needed. At visit 2, an endocrinologist consultant will give to the patient instructions for antidiabetic treatment titration according to [appendix 1](#).

Patients will be treated for 8 weeks with the study drug or placebo 10 mg/day every morning.

Washout period

Study subjects will stop study drug (empagliflozin/placebo) for 4 weeks and will crossover to the second drug at the end of this period. During this period patient's glucose level will be self monitored by a home device 3 times a day in the first week and thereafter once a week or as needed. Safety laboratory examinations, HbA_{1c}, device interrogation and resetting, Holter ECG and echocardiography will be performed at the end of this period (visit 3).

Second treatment period

Patients will crossover to empagliflozin or placebo treatment for a period of 8 weeks.

Evaluations consists of vital signs, laboratory assessments including pregnancy test for FCBP, patient's glucose level will be monitored by a home device 3 times a day in the first week and thereafter once a week or as needed. Device (ICD or CRTD/P) interrogation and 24h' Holter ECG in case of ICD/CRTD/P malfunction as a backup arrhythmia assessment and echocardiography.

Patients will be treated for 8 weeks with the study drug or placebo 10 mg/day every morning.

	
 9. BMI>50 10. Medical History of active cancer in the past 2 years. 11. History of recurrent UTIs or genital infections 12. Systolic blood pressure <90 mmHg. 13. Alcohol or drug abuse within 3 months of informed consent. 14. Premenopausal women with planned pregnancy or without adequate measures for birth-control. 15. Intake of an investigational drug in another trial within 30 days prior to intake of study medication in this trial or participating in another trial involving an investigational drug and/or follow-up

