4.2 Overall study design

The present study is a randomized, prospective, controlled, double blind, cross-over, pairwise, add on standard therapy, event driven study, comparing empagliflozin versus placebo on the ventricular arrhythmia burden in a blocked randomization stratified by ischemic versus non-ischemic cardiomyopathy and PVC burden at screening of $<$ or \geq to 4%.

Patients will be recruited from the congestive heart failure clinic of the study site and treated for up to 8 weeks with the study drug (or placebo) and then another 8 weeks with placebo (or study drug) with a washout period of 4 weeks between the two treatment periods. Potential study subjects will sign an informed consent prior to undergoing any study related procedure. Generally, study medications should be continued until intolerance. Treatment after completion of the study is at the discretion of the investigator.

Up to 128 patients are planned to be enrolled. Enrollment time of the study is one year.

This study encompass 4 periods for each study subject: screening period of 8 weeks, first treatment period of 8 weeks, washout period of 4 weeks and a second treatment period of 8 weeks. Expected duration of subject participation is 6-7 months.

Study assessments will be performed according the table of study procedures below. ([Table 2](#))

Screening / run in period

Patients will undergo screening for protocol eligibility within 56 days (8 weeks) of recruitment.

Subjects meeting all the inclusion criteria and do not meet any exclusion criteria will be enrolled after signing an informed consent.

Written informed consent must be obtained before any study specific medical procedures are performed. Evaluation consists of physical examination

including vital signs, laboratory-screening assessments including urine pregnancy test for FCBP, HbA_{1c}, device (ICD or CRTD/P) interrogation and echocardiography (if not done recently).

First treatment period

Randomization will take place after obtaining patient's informed consent and after fulfilling the inclusion and exclusion criteria. Patients will be assigned to empagliflozin or placebo treatment for a period of 8 weeks by a central randomization process.

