4.4 Study drug interruption or discontinuation

4.4.1 Discontinuation of study drug

The following events will be considered as reasons for drug discontinuation:

- Subject's request
- Intolerable grade 3/4 adverse drug reaction that is judged by the investigator to be either physically or psychologically detrimental to the patient.
- Any study drug interruption that exceeds 14 consecutive days.
- Patient's non-compliance with study procedures as evaluated by PI and/or sponsor as warranting therapy discontinuation.
- Other reasons regarded by the PI as warranting therapy discontinuation.
- Premature study termination as described below.
- Pregnancy. If a woman becomes pregnant during the treatment period of the study, she will immediately be withdrawn from the study and will be followed up until delivery.

The investigator should contact the subject either by telephone or through a personal visit or a responsible relative must be contacted to determine as completely as possible the reason for the withdrawal. A complete final evaluation at the time of the patient's withdrawal should be made with an explanation of why the patient is withdrawing. If the reason for removal of a patient from the study treatment is an adverse event or an abnormal laboratory test result, the principal specific event or test will be recorded on the case report form.

The section for "Study Completion" in the CRF must be completed for all patients. The reason for early discontinuation should be given, even if the patient refused to return for a final visit. Patients whose treatment is

discontinued prematurely due to significant adverse events (AEs) should continue to be followed until resolution of the AE, and the relevant sections of the CRF should be completed as appropriate. Patients who are discontinued due to clinically significant abnormalities in clinical laboratory results should continue to be evaluated until the abnormality resolves or is judged permanent. Patients lost to follow up should be recorded as such on the CRF. If patients refuse to return for these visits or are unable to do so, the patient should be considered off-study.

Subjects withdrawn from the study will not be replaced.

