4.5 Study Discontinuation

The patient or the investigator can decide to discontinue subject participation on study.

Possible reasons of premature study termination include:

- Death
- Participation in another investigational drug trial
- Loss to follow-up
- Patient withdrawal of consent
- Malfunction of CRTD/ICD.
- Clinical need to begin antiarrhythmic drug excluding beta blockers.
- Occurance of myocardial infarction.
- Sepsis as a consequence of UTI or genital infection.
- Administrative problems (of the whole study)
- Patient of investigator not compliant with study protocol.

- Occurrence of an AE which makes discontinuation desirable or necessary in the investigators' and/or the patients' opinion

In those cases, no patient follow-up will be recorded.

The section for "Study Completion" in the CRF must be completed for all patients. The reason for early discontinuation should be given, even if the patient refused to return for a final visit. Patients who discontinue prematurely due to significant adverse events (AEs) should continue to be followed until resolution of the AE, and the relevant sections of the CRF should be completed as appropriate. Patients who are discontinued due to clinically significant abnormalities in clinical laboratory results should continue to be evaluated until the abnormality resolves or is judged permanent.

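### Section 4.3.1 ties study drug to perceived benefit, against the protocol's other dosing rules, and no period 2 read-out is secured once drug stops (minor)

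*Combined protocol and SAP*

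**What the plan says.** **Dosing.** Section 4.3.1 provides study drug 10 mg once daily "if in the opinion of the investigator the patient is benefiting from treatment with this study drug" and there are no safety concerns. The sentence after it reads "Treatment will be withheld only in the case of limiting toxicities". The synopsis states "Patients will be treated for 8 weeks with the study drug or placebo 10 mg/day every morning" (the text of 4.2 has up to 8 weeks). Section 4.2 adds "Generally, study medications should be continued until intolerance", and section 4.4.2, repeated in 5.3.2, says "No study drug interruption is allowed unless for safety reasons".

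**Stopping drug.** Section 4.4.1 lists reasons such as patient request, intolerable grade 3/4 reactions, interruption beyond 14 days, non-compliance and pregnancy. It also has an open-ended entry: "Other reasons regarded by the PI as warranting therapy discontinuation". Lack of benefit is neither named nor excluded. On withdrawal, "A complete final evaluation at the time of the patient's withdrawal should be made". Later follow-up is written only for adverse events, laboratory abnormalities and pregnancy, and withdrawn subjects are not replaced.

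**Leaving the study.** Section 4.5 opens with "The patient or the investigator can decide to discontinue subject participation on study". It lists possible reasons and states that follow-up is not recorded in those cases, although adverse events and laboratory abnormalities are still followed.

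**Measurement and analysis.** Table 2 has device interrogation and counter reset at all five visits but does not say whether they continue off drug. Section 9.2.1 uses a paired t-test or signed-rank test unless carry-over is significant, in which case a mixed model applies. Section 9.1 calls the efficacy analysis as treated.

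**The concern.** Adjacent sentences in 4.3.1 give opposite instructions: one makes perceived benefit a condition of dosing, the other allows only toxicity as a reason to withhold. In a crossover each patient has to take both treatments whatever happened in period 1, so a benefit condition has no place.

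The principal investigator approves the PVC counter data before CRF entry (section 7.1), and echocardiography is done at visit 3. Much of the period 1 result can therefore be seen before the crossover at visit 4. If the clause encouraged a stop at that point under the open-ended reason in 4.4.1, and read-outs stopped too, the patient would have no period 2 value and would drop out of the primary test. The same gap exists for a stop for any other reason, which makes it the more important half of the point.

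**Working it through.** **1. Which dosing rule governs?** Toward continuing: the second sentence of 4.3.1, the fixed periods in the synopsis, 4.2 and 4.4.2. Toward a benefit condition: the one clause in 4.3.1. The clause cannot be applied literally at visit 2 or visit 4, because the drug of that period has not yet been taken. The likely explanation is leftover wording.

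**2. Does a drug stop lose the pair?** Efficacy is read at visits 3 and 5 (7.1). A clean period 2 value needs the counter reset at visit 4 and the read-out at visit 5. Section 4.4.1 does not require either after withdrawal. A patient with period 1 only meets the ITT definition in 9.2 (one post-baseline assessment) but contributes no within-patient difference to the paired test.

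**3. Reproduce the planned size.** Inputs from 9.1: difference 10, SD of differences 40, two-sided alpha 0.05, power 80%, 64 per sequence.

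N = (40 × (1.960 + 0.842) / 10)² = 11.208² = 125.6, so 126. The plan has 128. Exact t power at 128 is 80%. The margin of two patients leaves no visible dropout allowance.

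**4. Pairs lost at random.** The noncentrality is 10 / (40/√N) = √N / 4. The loss rates are assumptions.

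| Assumed loss | Pairs left | √N / 4 | Power |
|---|---|---|---|
| 0% | 128 | 2.828 | 80% |
| 5% | 122 | 2.761 | 78% |
| 10% | 115 | 2.681 | 76% |
| 20% | 102 | 2.525 | 71% |

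**5. Outcome-dependent loss, 10% of patients, blinded to treatment.** By simulation:

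- Normal data, paired t-test, within-patient correlation 0.3 to 0.7. Power is 75% if stopping correlates 0.5 with the period 1 value, 73% if it falls on the worst change from baseline, and 72–74% if it falls on the worst period 1 values. That is 1 to 4 points below random loss, with the estimate between -9.9 and -9.1. At correlation 0, the worst-value rule gives about 70% and -8.8.
- Lognormal burdens (log-scale between/within SDs 0.8/0.5, 1.0/0.6, 1.0/1.0), signed-rank test. Losing the worst period 1 values gives 74%, 75% and 71%, against 73%, 75% and 73% for random loss. Paired t power rose to 83–85%. Losing the worst change from baseline costs 0 to 2 points beyond random loss under either test.

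The extra cost, and even its sign, therefore depends on the distribution and the test.

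**6. Type I error.** Null rejection was 4.5–5.2% in the normal-data simulations at correlations 0.3 to 0.7, and no higher than 5% at correlation 0. The reason is general. With no treatment effect and a blinded stop, randomisation alone sets the sign of each retained treatment difference, so the differences stay centred on zero.

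**7. Keep the read-outs instead.** If 10% (13 patients) skip period 2 drug but are read out and analysed as randomised, and half of them were due empagliflozin, the dilution is 6.5/128 × 10 = 0.5, giving an estimate of about -9.5. The simulated estimate is -9.36 to -9.45, because patients with a poor period 1 had more often taken placebo first. Power is 76%. At 20% with the worst period 1 values, power is 71% and the estimate -8.8.

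**The case against.** The strongest reply is that this is a drafting slip with no practical effect. Every other dosing rule says continue, 4.4.1 does not list lack of benefit, and its open-ended entry would allow the stop even without the clause. The design also works against the feared behaviour: after visit 3 the patient takes placebo for 4 weeks and then the other treatment, so a blinded investigator who sees a poor period 1 has reason to let the switch happen. NT-proBNP blood is only collected at visit 3, and nothing says the result is available then. Section 4.5 concerns leaving the study, not stopping drug. Section 4.4.1 also treats patients who will not return for visits as off-study, which suggests that stopping drug does not by itself end visits, although that sentence may refer only to adverse-event follow-up.

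Most of this stands, and it is why the point is minor. It does not remove the contradiction in operative dosing text, and it does not supply the missing rule for period 2 read-outs after a stop. The reply is also right that steps 2 and 3 of the fix address stopping in general, not this clause alone. Their power gain is modest: at 10%, 76% against 72–75% under the normal-data rules at correlation 0.3 to 0.7, and nothing over random loss.

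**Conclusion.** The benefit condition in 4.3.1 contradicts the protocol's other dosing rules and should go. The more useful finding is that a drug stop for any reason may cost the pair. Losing 5%, 10% or 20% of pairs takes power from 80% to about 78%, 76% or 71%. These rates are assumed, and the figures use the plan's own difference of 10 and SD of 40.

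A reader might infer two stronger claims that the documents do not support. One is that the protocol tells investigators to stop patients who do not improve; no section does, and most point the other way. The other is that selective stopping could produce a false positive or a large bias. With blinded decisions it does not raise type I error. In the normal-data simulations the estimate moved toward zero, and the extra power cost was small at correlations of 0.3 to 0.7 (about 6 points at correlation 0) and uncertain in sign once skewed data and the signed-rank test are considered. These statements rest on the blind holding.

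Severity: minor, a cheap improvement.

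**What to change.** 1. In 4.3.1, delete the benefit condition. State that drug continues for the full 8 weeks of each period unless a 4.4.1 criterion is met, and that lack of perceived benefit is not such a criterion, including under the open-ended entry.
2. Amend 4.4.1 and 4.5 so that consenting patients who stop drug still have the scheduled device read-outs and counter resets through visit 5.
3. In 9.1, replace the as-treated statement with analysis of each period under its randomised treatment.

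The cost is rewording four sections and a few read-outs at visits already in Table 2. The downside is the dilution from off-drug time in step 7 of the working. In return, the primary comparison no longer depends on why a patient stopped.
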